### 9.3.4 Management of hepatitis B

Table 6 provides details of monitoring and prophylactic therapy according to the baseline results of viral load and serologic markers testing.

## Memorial Sloan-Kettering Cancer Center IRB Protocol

IRB#: 08-123 A(8)

**Table 6 Action to be taken for positive baseline hepatitis B results**

Test	Result	Result	Result	Result
HBV-DNA	+	+ or -	-	-
HBsAg	+ or -	+	-	-
HBs Ab	+ or -	+ or -	+ and no prior HBV vaccination	+ or - or + with prior HBV vaccination
HBc Ab	+ or -	+ or -	+ or -	+
Recommendation	Prophylaxis treatment should be started 1-2 weeks prior to first dose of study drug  Monitor HBV-DNA approximately every 4 weeks			No specific action

Antiviral prophylaxis therapy should continue for at least 4 weeks after last dose of study drug.

For patients who have already been randomized and received study drug prior to the approval of the amendment, the same process should be followed at the patient's next visit. The first HBV-DNA result would be regarded as baseline.

For hepatitis B reactivation, definition and management guidelines, see Table 3-2 Guidelines for management of hepatitis B.

## Memorial Sloan-Kettering Cancer Center IRB Protocol

**IRB#: 08-123 A(8)**

**Table 7 Guidelines for management of hepatitis B**

HBV reactivation (with or without clinical signs and symptoms)*	
For patients with baseline results: Positive HBV-DNA OR positive HBsAg  reactivation is defined as: [Increase of 1 log in HBV-DNA relative to baseline HBV-DNA value OR new appearance of measurable HBV-DNA] AND ALT elevation x 5 ULN	Treat: Start a second antiviral AND Interrupt study drug administration until resolution: • $\leq$ grade 1 ALT (or baseline ALT, if $>$ grade 1) and • $\leq$ baseline HBV-DNA levels  If resolution occurs within <math>\leq</math> 28 days, study drug should be re-started at one dose level lower, if available. If the patient is already receiving the lowest dose of study drug according to the protocol, the patient should restart at the same dose after resolution. Both antiviral therapies should continue at least 4 weeks after last dose of study drug. If resolution occurs <math>></math> 28 days, patients should discontinue study drug but continue both antiviral therapies at least 4 weeks after last dose of study drug.
For patients with baseline results: Negative HBV-DNA and HBsAg AND [Positive HBs Ab (with no prior history of vaccination against HBV), OR positive Hbc Ab]  reactivation is defined as: New appearance of measurable HBV-DNA	Treat: Start first antiviral medication AND Interrupt study drug administration until resolution: • $\leq$ baseline HBV-DNA levels  If resolution occurs within <math>\leq</math> 28 days, study drug should be re-started at one dose level lower, if available. If the patient is already receiving the lowest dose of study drug according to the protocol, the patient should restart at the same dose after resolution. Antiviral therapy should continue at least 4 weeks after last dose of study drug. If resolution occurs <math>></math> 28 days, patients should discontinue study drug but continue antiviral therapy at least 4 weeks after last dose of study drug.

\* All reactivations of hepatitis B are to be recorded as grade 3 (CTCAE v 3.0 Metabolic Laboratory/Other: Viral Re-activation), unless considered life threatening by the investigator; in which case they should be recorded as grade 4 (CTCAE v 3.0 Metabolic Laboratory/Other: Viral Re-activation). Date of viral reactivation is the date on which both DNA and ALT criteria were met (e.g. for a patient who was HBV-DNA positive on 01-JAN-10 and whose ALT reached  $\geq$  5  $\times$  ULN on 01-APR-10, the date of viral reactivation is 01-APR-10).

### 9.3.5 Hepatitis C management

The following two categories of patients should be monitored every 4 weeks for HCV reactivation:

- Patients with detectable HCV RNA-PCR test at baseline.
- Patients known to have a history of HCV infection, despite a negative viral load test at baseline (including those that were treated and are considered 'cured')

For definition of hepatitis C reactivation and the management guidelines, see Table 8.

## Memorial Sloan-Kettering Cancer Center IRB Protocol

IRB#: 08-123 A(8)

**Table 8 Guidelines for management of hepatitis C**

HCV reactivation*	
For patients with baseline results: Detectable HCV-RNA, reactivation is defined as: ALT elevation x 5 ULN	Discontinue study drug
For patients with baseline results: Knowledge of past hepatitis C infection with no detectable HCV-RNA, reactivation is defined as: New appearance of detectable HCV-RNA	Discontinue study drug

\* All reactivations of hepatitis C are to be recorded as grade 3 (CTCAE v 3.0 Metabolic Laboratory/Other: Viral Re-activation), unless considered life threatening by the investigator; in which case they should be recorded as grade 4 (CTCAE v 3.0 Metabolic Laboratory/Other: Viral Re-activation).

All interruptions or changes to study drug administration must be recorded.

It will be documented whether or not each patient completed the clinical study. If, for any patient, either study treatment or observations are discontinued, the reason will be recorded.

### 9.4 Treatment Compliance

Records of study medication used, dosages administered, and intervals between visits will be recorded during the study. Drug accountability will be noted and patients will be asked to return all unused study medication.

### 9.5 Concomitant Medications

Patients will be instructed not to take any additional medications (including over-the-counter products) during the course of the study without prior consultation with the investigator. At each visit, the investigator will ask the patient about any new medications he/she is or has taken after the start of the study drug.

All Concomitant medications/Significant non-drug therapies taken  $\leq$  30 days prior to start and after start of study drug, including physical therapy and blood transfusions, should be recorded.

The following restrictions apply during the entire duration of the study:

- No other investigational therapy should be given to patients.
- No anticancer agents other than the study medication should be given to patients. If such agents are required for a patient then the patient must first be withdrawn from the study.
- Growth factors (e.g. G-CSF, GM-CSF, erythropoietin, platelets growth factors etc.) are not to

## Memorial Sloan-Kettering Cancer Center IRB Protocol

**IRB#: 08-123 A(8)**

be administered prophylactically but may be prescribed by the investigator for rescue from severe hematologic events if this is thought to be appropriate.

- Concurrent administration of Everolimus and strong CYP3A4 inhibitors (such as ketoconazole, itraconazole, ritonavir) and inducers (such as rifampin, rifabutin) should be avoided. Provided there is no alternative treatment available, patients should be closely monitored for potential toxicities.
- Concurrent administration of Everolimus and moderate CYP3A4 inhibitors (such as erythromycin, fluconazole, calcium channel blockers, benzodiazepines) and moderate CYP3A4 inducers (e.g. carbamazepine, phenobarbital, phenytoin) should also be avoided if possible, or used subject to caution (e.g. increased frequency of safety monitoring, temporary interruption of Everolimus).
- Competitive inhibition could occur when Everolimus is combined with drugs which are also CYP3A4 substrates. Caution should be exercised in such cases.
- Co-administration with substrates, inducers, or inhibitors of P-glycoprotein should be avoided, if possible, or used subject to caution (e.g. increased frequency of safety monitoring, temporary interruption of Everolimus).
- Grapefruit and grapefruit juice affect cytochrome P450 and P-glycoprotein activity and should therefore be avoided.
- In addition, patients should avoid Seville oranges and star fruit as well as the juice of these fruits, which are potent CYP3A4-inhibitors.
- No chronic treatment with systemic steroids or immunosuppressive agents except corticosteroids with a daily dosage equivalent to prednisone  $\leq 20$  mg should be administered. Patients receiving corticosteroids must have been on a stable dosage regimen for a minimum of 4 weeks prior to the first treatment with Everolimus. Topical or inhaled corticosteroids are allowed.
- Everolimus may affect the response to vaccinations, making the response to the vaccination less effective. Live vaccines should be avoided while a patient is treated with Everolimus.

Oral anticoagulants such as warfarin are CYP2C9 substrates; as such, no interaction with Everolimus is expected. However, drug-drug interaction studies between macrolide antibiotics and warfarin have produced mixed outcomes and the disparity in these findings has led to the conclusion that multiple factors may alter the clearance of warfarin. The coadministration of Everolimus and oral anticoagulants is possible but should be subject to verification of coagulation (INR) once steady state is reached (after one week's treatment).

Examples are provided in Table 6. A comprehensive list of cytochrome P450 isoenzymes and CYP3A4 inhibitors, inducers, and substrates can be found at <http://medicine.iupui.edu/flockhart>. This website is continually revised and should be checked frequently for updates.

## Memorial Sloan-Kettering Cancer Center IRB Protocol

IRB#: 08-123 A(8)

**Table 6. Examples of clinically relevant drug interaction: substrates, inducers and inhibitors of isoenzyme CYP3A.**

Substrates (competitive inhibition)	
Antibiotics  : clarithromycin* erythromycin telithromycin* Anti-arrhythmics: quinidine Benzodiazepines: alprazolam diazepam midazolam triazolam Immune Modulators: cyclosporine tacrolimus (FK506) HIV Protease Inhibitors: indinavir* ritonavir* saquinavir* Prokinetic: cisapride Antihistamines: astemizole chlorpheniramine 	Calcium Channel Blockers: amlodipine diltiazem felodipine nifedipine nisoldipine nitrendipine verapamil HMG CoA Reductase Inhibitors  : atorvastatin cerivastatin lovastatin simvastatin Miscellaneous: aprepitant buspirone haloperidol methadone pimozide quinine sildenafil tamoxifen trazodone vincristine
Inducers	
Carbamazepine Phenobarbital Phenytoin* Rifabutin*	Rifampin* St John's wort Troglitazone
Inhibitors	
Amiodarone Atanzavir Cimetidine Ciprofloxacin Clarithromycin Conivaptan* Darunavir Delavirdine Diltiazem Erythromycin Fluconazole Fluvoxamine* Grapefruit juice Sevilla orange Posaconazole*	Indinavir Itraconazole* Ketoconazole* Lopinavir* Voriconazole* Posaconazole* Mibepradil* Nefazodone* Nelfinavir* Troleandomycin* Verapamil Voriconazole* Imatinib Tofisopam

Based on: Ingelman-Sundberg M, Human drug metabolising cytochrome P450 enzymes: properties and polymorphisms, Naunyn Schmiedebergs Arch Pharmacol. 2004 Jan;369(1):89-104. [http://www.medicine.iupui.edu/flockhart/clinlist.htm as of July 13, 2006], Internal Clinical Pharmacology Drug-drug interaction (DDI) memo, updated Dec. 2, 2009, which summarizes DDI data from three sources including the FDA's "Guidance for Industry, Drug Interaction Studies, the University of Washington's Drug Interaction Database, and Indiana University School of Medicine's Drug

## Memorial Sloan-Kettering Cancer Center IRB Protocol

**IRB#: 08-123 A(8)**

---

### Interaction Table. "

\* asterisk denotes strong inhibition/induction

Please note:

- strong inhibitor implies that it can cause  $\geq 5$ -fold increase in AUC or  $\geq 80\%$  decrease in clearance of sensitive CYP substrates
- moderate inhibitor implies that it can cause 2- to 5-fold increase in AUC values or 50-80% decrease in clearance of sensitive CYP substrates.

(Distinction is not always categorical as interaction can vary according to conditions).

1. Macrolide antibiotics: Azithromycin is not a CYP3A substrate. Therefore, it may be employed where antibiotic therapy with a macrolide is desirable in a patient being treated with Everolimus.
2. Statins: Atorvastatin and pravastatin may be associated with Everolimus, since a PK interaction study has shown that there is no relevant PK interaction.

---

## Memorial Sloan-Kettering Cancer Center IRB Protocol

IRB#: 08-123 A(8)

### 10.0 EVALUATION DURING TREATMENT/INTERVENTION

**Table 7. Schedule of Events**

Procedure	Screening		Cycle 1			Additional Cycles (Years 1-4)		Additional Cycles (Years 5+)		Post Treatment/ Withdrawal 	Survival Follow-up
	≤ 30 Days Prior to Dosing	≤ 14 Days Prior to Dosing	Day 1 (± 3)	Day 14 (± 3)	Day 28 (± 3)	Day 1 (± 3)	Day 28 (± 3)	Day 1 (± 3)	Day 56 (± 3)		
Informed Consent		X									
Medical History		X									
Physical Examination, KPS		X	(X) 	X		X		X 		X	
Lab Studies											
Pregnancy Test 		X									
Hematology 		X	(X) 	X		X		X 		X	
Biochemistry 		X	(X) 	X		X		X 		X	
PT/PTT		X									
Fasting Lipids 		X	(X) 			X		X 		X	
HBV-DNA, HBsAg, HBs Ab, HBs Ab, HCV-RNA-PCR 	X										
HBV DNA, HCV RNA-PCR 			X			X		X		X	
Other Assessments											
12-lead EKG	X										
Pulmonary Function Tests	X										
Disease Assessment/Tumor measurements 	X						X 		X 	X	
Adverse Events 			X	X		X		X 		X	
Concomitant Medications		X	X	X		X		X 		X	
Treatment compliance 					X		X		X		
Everolimus 			X →	→	→	→	→	→	→		
Survival Status 											X
Tumor Tissue Evaluation 	X										

(X) – if applicable    X → - start and continue treatment    → - continue treatment

## Memorial Sloan-Kettering Cancer Center IRB Protocol

IRB#: 08-123 A(8)

Footnotes for Schedule of Events	
1. Complete blood count (CBC) with differential and platelets	
2. Comprehensive panel (i.e. serum electrolytes including sodium, potassium, chloride, bicarbonate, phosphorus, calcium, glucose, blood urea nitrogen, creatinine, SGOT (AST), SGPT (ALT), alkaline phosphatase, total bilirubin, total protein, albumin, uric acid).	
Fasting Lipids include triglycerides, total cholesterol, HDL and LDL.	
3. Disease Assessment/Tumor Measurements: Re-staging imaging studies will be performed after every two cycles of treatment (1 cycle = 4 weeks) during the first five years of treatment and after study completion or withdrawal. Imaging studies should be performed during weeks 7 or 8. The same imaging studies performed at baseline (e.g., CT or MRI) should be performed throughout the study, when possible. Baseline chest CT or chest x-ray must be performed. If chest CT or chest x-ray is not part of the disease assessment, it must be repeated every 2 months. Bone x-ray(s)/scan to be performed if bone metastases are present.	
4. Adverse Events: Patients must be followed for adverse events from the first day of study treatment until at least 28 days after the last on-study treatment administration, or until all serious or study drug-related toxicities have resolved or are determined to be "chronic" or "stable," whichever is later. Serious adverse events should be monitored and reported as described in the protocol.	
5. Post-study survival status: Follow-up survival information will be collected for all patients by clinic visit or telephone contact approximately every 6 months for up to 2 years from the date of first dose of Everolimus. Patients will be followed until disease progression and/or death.	
6. Physical Examination/Hematology/Biochemistry/Fasting Lipids: Physical Examination/ Hematology/ Biochemistry/Fasting Lipids on Cycle 1 Day 1 is not required if performed within 7 days of Day 1 unless clinically indicated.	
7. Post Treatment/Withdrawal: This visit will take place 1 month after the last dose of study drug. Patients with ongoing study drug-related toxicities should be followed as dictated in footnote 4. These patients should be followed at the interval deemed appropriate by their study physician.	
8. Everolimus: Everolimus will be orally self-administered, once daily in the morning. Patients will receive a prescription for a 4-week supply of drug at the beginning of each cycle during their first five years of treatment. After five years of treatment, patients will receive a prescription for an 8-week supply of drug at the beginning of every other cycle. The Everolimus drug bottles (including any unused capsules) will be returned to the clinic for drug accountability at each study visit.	
9. Serum or urine test must be performed for all women of childbearing potential.	
10. Pre-treatment tumor tissue specimens for all patients will be analyzed using immunohistochemistry for markers including those of an activated mTOR pathway including phospho-S6 and phospho-4E BP1. Note that the study will not require research biopsies. -	
11. Treatment Compliance: At the start of each cycle, patients will be given a Pill Diary and asked to record the time, date, concomitant drugs, and side-effects of each dose of Everolimus taken.	
12. All patients should be screened for hepatitis risk factors and any past illnesses of hepatitis B and hepatitis C. It is highly recommended that patients with positive HBV-DNA or HBsAg are treated prophylactically with an antiviral for 1-2 weeks prior to receiving study drug. The antiviral treatment should continue throughout the entire study period and for at least 4 weeks after the last dose of study drug. Patients with viral hepatitis C risk factors should be screened for HCV RNA-PCR.	
13. Patients on antiviral prophylaxis treatment or positive HBV antibodies should be tested for HBV-DNA according to study visit schedule. Patients with positive HCV-RNA PCR or a history of past infection, even if treated and considered 'cured' – should be followed by HCV-RNA PCR according to visit schedule.	

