### 1.0 PROTOCOL SUMMARY AND/OR SCHEMA

This is an open-label Phase II study of Everolimus (RAD001) in patients with progressive advanced/metastatic urothelial carcinoma that have progressed despite treatment with prior cytotoxic chemotherapy. The primary objective of the study is to measure the 2-month PFS rate of Everolimus (RAD001) as determined by RECIST. Everolimus will be administered at a dose of 10 mg orally once daily continuously. Intra-patient dose reduction may be required depending on the type and severity of the individual toxicity encountered. Re-staging imaging studies will be performed after every two cycles of treatment (one cycle = 4 weeks) during the first five years of treatment, and after every 3-6 cycles of treatment thereafter. Patients may continue on study as long as they are tolerating therapy and are free of disease progression.

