## Memorial Sloan-Kettering Cancer Center IRB Protocol

**IRB#: 08-123 A(8)**

The start of the next cycle may be delayed if additional time is required for the patient to recover from Everolimus-associated toxicity experienced during the previous cycle. However, imaging will occur at regular intervals. The study investigator may implement dose suspension or reduction in order to ensure patient safety (see section 9.2).

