### 9.3.3 Management of non-infectious pneumonitis

Both asymptomatic radiological changes (grade 1) and symptomatic non-infectious pneumonitis (grade 2 = not interfering with activities of daily living or grade 3 = interfering with activities of daily living and oxygen indicated) have been noted in patients receiving Everolimus therapy. Non-infectious pneumonitis has been associated with Everolimus and other mTOR inhibitors (Atkins 2004). All patients are required to undergo baseline/pretreatment pulmonary function tests and will be excluded from study treatment if TLC  $<50\%$  predicted, FVC  $<50\%$  predicted, or DLCO  $<40\%$  predicted. In order to monitor for asymptomatic (grade 1) non-infectious pneumonitis during study treatment, a chest CT scan or chest x-ray is required in addition to the monthly radiological tumor examinations. Additional chest CT scans may be performed when clinically necessary. If non-infectious pneumonitis develops, a consultation with a pulmonologist should be considered. If the patient develops grade 3 pneumonitis, treatment with Everolimus should be interrupted and the patient should be treated as medically indicated (short course corticosteroids, oxygen, etc).

Management of non-infectious pneumonitis suspected to be associated with Everolimus and dose modification instructions are provided in Table 5.

The attribution of changes on interval chest imaging will be recorded as related, possibly related, or unrelated to study drug.

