### 14.0 BIOSTATISTICS

The purpose of this study is to assess the efficacy of Everolimus in patients with progressive urothelial cancer who have received prior cytotoxic chemotherapy. Historically, patients in this setting experience a median time to progression of 2-3 months (as illustrated in Section 3.1). Thus, the primary endpoint of this study will be the proportion of patients who are progression-free after two months on-study.

The sample size and stopping rules will be determined according to Simon's Minimax two-stage design. A two-month progression free survival rate of 50% would be considered not promising, while a 70% two-month PFS rate would be considered promising. In Stage 1 of the trial, 23 evaluable patients will be accrued to the study. If twelve or more patients demonstrate progression on imaging after two months on-study, the study will be terminated early and declared to have a negative result. If 13 or more patients are progression-free at two months, enrollment will be extended to accrue a total of 37 patients. If 24 or more patients are progression-free after their two-month scan (i.e. after Stage 2), the treatment will be declared effective and worthy of further testing.

**Patients will be considered inevaluable for the primary objective (PFS at 2 months) if they receive ≤one cycle of protocol therapy and are discontinued from protocol treatment for either rapid clinical deterioration related to progression of disease or adverse events unrelated to Everolimus. Patients with still be evaluable for toxicity assessment.**

For the purposes of this study, the Type I (false acceptance of a non-promising therapy) and Type II (false rejection of a promising therapy) error rates have been set at 0.05 and 0.20, respectively. This statistical design would effectively discriminate between two-month PFS rates of <50% and >70% and yields 80% probability of a positive result if the true two-month PFS rate is >70%. It yields 95% probability of a negative result if the true two-month PFS rate is <50%. The probability of early stopping under the null hypothesis is 66%.

The secondary endpoint of response rate will be estimated as the proportion of patients meeting the criteria outlined in Section 3.4.2.3 for a complete response or partial response. This proportion will be reported along with its binomial confidence interval.

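### The timing of the primary two-month scan contradicts itself: one instruction allows it up to 13 days before 8 weeks, and no rule says how an early scan is counted

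*Combined protocol and SAP*

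**What the plan says.** Section 14.0 defines the primary endpoint as "the proportion of patients who are progression-free after two months on-study" and sets the null: "A two-month progression free survival rate of 50% would be considered not promising". The final decision is tied to a scan: "If 24 or more patients are progression-free after their two-month scan", the drug is declared effective. Neither two months nor the two-month scan is expressed in days.

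The timing of that scan appears in several places:

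- **Sections 1.0 and 4.3:** "Re-staging imaging studies will be performed after every two cycles of treatment (one cycle = 4 weeks"). Taken from the start of treatment, that is day 56 or just after.
- **Section 10.0, Schedule of Events, footnote 3:** the same two-cycle interval, followed at once by "Imaging studies should be performed during weeks 7 or 8".
- **Section 10.0, Schedule of Events, table:** the tumor assessment is marked under Day 28 (±3) of the additional cycles.
- **Section 9.2:** "The start of the next cycle may be delayed if additional time is required for the patient to recover", but "However, imaging will occur at regular intervals".
- **Section 9.3.3:** chest imaging is required "in addition to the monthly radiological tumor examinations", although the Schedule marks no tumor assessment at Cycle 1 Day 28.

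Section 12.4.5 runs PFS from the start of treatment to progression or death and treats death before documented progression as failure. It does not link that definition to the yes/no count in section 14.0.

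**The concern.** A site that follows footnote 3 to the letter can scan a patient on day 43 and have complied. If that scan is clean, the patient has had the only restaging scan due around two months, and the next is about 8 weeks later. Progression visible only on imaging between week 7 and the landmark would normally go unseen unless extra imaging is done. The observed proportion can then exceed the proportion truly progression-free at two months, while the 50% null and the cut-off of 24 stay fixed.

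The whole efficacy conclusion is one count in 37 patients, so one or two patients read early could decide the result. Two sites or readers could also apply different windows, each with support in the text, and obtain different counts from the same patients.

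**Working it through.** **1. Windows in study days.** Take day 1 as the first day of treatment and assume cycle 2 starts on day 29.

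- Weeks 7 or 8: week 7 is days 43-49 and week 8 is days 50-56, so 14 days in all.
- Day 28 (±3) of cycle 2: 28 + 28 = 56, so days 53-59.
- Common to both: days 53-56. Days 43-52 (10 of the 14) are allowed only by the footnote sentence. Days 57-59 are allowed only by the table.

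**2. The plan's own design.** Inputs from section 14.0: stage 1 has 23 patients, continue with 13 or more progression-free; total 37, positive with 24 or more; rates 50% and 70%.

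P(positive) = Σ over x = 13 to 23 of Bin(x; 23, p) × P(Bin(14, p) ≥ 24 − x)

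- p = 0.50: P(positive) = 0.048. Early stopping is P(Bin(23, 0.5) ≤ 12) = 0.661.
- p = 0.70: P(positive) = 0.801.

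These match the stated 5%, 80% and 66%. The sample-size arithmetic is sound.

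**3. Direction.** The probability of being progression-free cannot rise with time. Reading a patient before the landmark therefore gives an expected proportion at or above the landmark proportion.

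**4. Size, as an illustration.** Assume that two months means 8 weeks, that PFS is exponential and that the true rate at day 56 is 50%. Then the probability of being clean on day d is p(d) = 0.5^(d/56). Average p(d) over the days on which scans fall, and put the mean into the formula in step 2. For days 53-56 the mean is (0.5189 + 0.5125 + 0.5062 + 0.5000)/4 = 0.509.

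| Scans fall evenly on | Mean p | P(positive) |
|---|---|---|
| days 53-59 (Schedule table) | 0.500 | 4.8% |
| days 53-56 (both windows) | 0.509 | 6.1% |
| days 50-56 (week 8) | 0.519 | 7.6% |
| days 43-56 (weeks 7 and 8) | 0.543 | 13% |
| day 49 only | 0.545 | 13% |

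With half the scans on day 49 and half on day 56, the mean is (0.545 + 0.500)/2 = 0.523 and P(positive) is 8.3%.

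Over days 43-56 the expected number of extra apparent successes is 37 × (0.5426 − 0.5) = 1.6.

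**5. How close the decision is.** At a true 50% rate, trials that pass with exactly 24 or 25 successes make up (0.0249 + 0.0133)/0.0482 = 79% of all passes.

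**6. Power under the Schedule's window.** With a true day-56 rate of 70%, the mean of 0.7^(d/56) over days 53-59 is 0.700 and power is 80.1%.

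**The case against.** The strongest reply is that the protocol never says a clean week-7 scan is a two-month success. Section 14.0 speaks of patients progression-free after two months, and its stage 1 stopping wording refers to progression seen on imaging after two months. Under section 12.4.5, a death or a documented progression between week 7 and the landmark could still be a failure. This stands. A reader might infer that early clean scans are counted as successes by rule, but the text supports only that no rule covers them. It does not remove the gap, because progression that nobody images is not documented.

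Second, the conflict is partial. Days 53-56 satisfy both instructions, and a scan on day 56 produces no inflation if two months means 8 weeks. The 13% needs scans spread over all 14 days, or all on day 49, and nothing in the documents gives the share done in week 7. This stands too.

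Third, a reader might conclude that the trial is biased in its favor against historical chemotherapy. The documents cannot show that. The 50% null comes from historical medians of 2-3 months, which were also read at scans on schedules that are not given. Only bias relative to a literal two-month rate can be shown.

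Fourth, some of the discrepancies are minor. Section 9.2 largely handles delayed cycles by keeping imaging at regular intervals, and the monthly wording in section 9.3.3 belongs to pneumonitis monitoring. Both are tidying matters.

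The meaning of two months also matters. If it meant 60.875 days, the Schedule's days 53-59 would themselves give 9.4% under the same assumptions. The 4-week cycles make 8 weeks the natural reading, but section 14.0 should say so.

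**Conclusion.** Wrong as written. Footnote 3 contradicts itself and the Schedule table, and section 14.0 does not settle which window governs the primary count. Week 7 meets neither the two-cycle interval nor the Day 28 (±3) column. This finding rests on the text alone.

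The size is conditional. With exponential PFS, a true 8-week rate of 50% and an even spread of scans within each window, the false-positive probability runs from 4.8% under the Schedule's window to 13% under weeks 7 and 8. It would be wrong to report 13% as the trial's actual error rate, because that depends on scan dates and a PFS shape the documents do not give. It would also be wrong to conclude that the stated design is miscalculated: it reproduces exactly. What is missing is one window and one counting rule for the only efficacy decision.

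**What to change.** 1. In section 14.0, define the two-month landmark once, as 8 weeks (day 56) from the start of treatment.
2. Delete the weeks 7 or 8 sentence from footnote 3. Use the Schedule's existing tolerance, day 56 ±3, for the primary scan, and bring sections 1.0, 4.3, 9.3.3 and 10.0 into line with it.
3. State that progression or death documented before the landmark is a failure.
4. State how a patient whose only scan is clean and falls before the window is counted. One option is success if the next scheduled scan is still free of progression and failure otherwise. Add a sensitivity analysis making the other choice.

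Keep 24 of 37 and N = 37. If scans fall evenly around day 56, the error rate stays at 4.8% and power at 80.1%.

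The cost is a few changed sentences, with no added patients or scheduled scans. Some scans move about a week later, so some progressions are documented later. Under the option in item 4, a patient scanned too early may leave the stage 1 count open until the next scan, about 8 weeks on.
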